9.5 Instruction for initiation of a new cycle

A new course of treatment may begin on the scheduled Day 1 of a new cycle if:

- Absolute neutrophil count (ANC) ≥ 750 cells/mm³
- Platelets count $\geq 50,000$ /mm³
- Any other drug-related adverse events that may have occurred have resolved to \leq grade 2 severity.

If these conditions are not met on Day 1 of a new cycle, the subject will be evaluated weekly and a new cycle of treatment will not be initiated until the toxicity has resolved as described above. If the toxicity does not resolve within four weeks, the patient will be taken off the study. If the dosing of clarithromycin, lenalidomide or dexamethasone was halted during the previous cycle and was restarted with a one-level dose reduction without requiring an interruption for the remainder of the cycle, then that reduced dose will be initiated on Day 1 of the new cycle. If the dosing of clarithromycin, lenalidomide or dexamethasone was omitted for the remainder of the previous cycle or if the new cycle is delayed due to toxicity newly encountered on the scheduled Day 1, then the new cycle will be started with dose modifications as described in Section 9.6 and Table 2.

If the start of a new cycle is delayed more than 4 weeks, the patient will be removed from the protocol.

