9.6 Dose Modification

Doses of study medications will be modified for toxicity as listed below in Tables 1, 2a, and 2b. Doses must be adjusted for adverse events deemed related to study drug by the investigator. Doses may be adjusted for adverse events related to study medications not listed below at the discretion of the investigator.

Unless otherwise noted, other drugs in the regimen should be continued when the dosing of one or more drugs is delayed due to toxicity.

During BiRd therapy, if toxicity occurs that would indicate an interruption in treatment, the toxicity should be attributed to one or more drugs in the BiRD regimen and dose modifications instituted as instructed in the “Action” column of the table below based on attribution. During maintenance therapy, if toxicity occurs that would indicate a lenalidomide dose modification, toxicity should be attributed to lenalidomide and dose modifications instituted as instructed in the “Action” column of the table below based on attribution.

Table 1: Dose Reduction Steps:

Lenalidomide Dose Reduction

Starting Dose	Lenalidomide PO 25mg/day on days 1-21 of a 28 day cycle
Dose Level -1	Lenalidomide PO 15mg/day on days 1-21 of a 28 day cycle
Dose Level -2	Lenalidomide PO 10 mg/day on days 1-21 of a 28 day cycle
Dose Level -3	Lenalidomide PO 5 mg/day on days 1-21 of a 28 day cycle
Dose Level -4	Lenalidomide PO 5 mg every other day for on days 1-21 of a 28 day cycle

Dexamethasone Dose Reduction

Starting Dose	40 mg PO on days 1, 8, 15 and 22 of a 28 day cycle
Dose Level -1	20 mg PO on days 1, 8, 15 and 22 of a 28 day cycle
Dose Level -2	8 mg PO on days 1, 8, 15 and 22 of a 28 day cycle
Dose Level -3	8 mg PO on days 1 and 15 of a 28 day cycle
Dose Level -4	4 mg PO on days 1 and 15 of a 28 day cycle

Clarithromycin Dose Reduction

Starting Dose	500 mg BID PO days 1-28 of a 28 day cycle
Dose Level -1	250 mg BID PO days 1-28 of a 28 day cycle

Dose Level -2	250 mg PO daily on days 1-28 of a 28 day cycle
Dose Level -3	250 mg PO daily on days odd days of a 28 day cycle
Dose Level -4	Discontinue drug

Table 2a: RD Dose Modification Instructions

Toxicity	NCI Toxicity Grade	Action

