Diarrhea	≥ Grade 3	
 • Hold (interrupt) clarithromycin until ≤ grade 1, then reduce dose to 250 mg twice daily
Dyspepsia	≥ Grade 3	
 • Hold (interrupt) clarithromycin and dexamethasone dosing until ≤ grade 1 • Reduce dexamethasone OR clarithromycin by 1 dose level based on attribution and restart dexamethasone and clarithromycin
Anaphylaxis or Hepatic failure	≥ Grade 3	
 • Discontinue clarithromycin and patient is off study
Loss of appetite or Nausea	≥ Grade 3	
 • Hold (interrupt) clarithromycin until ≤ grade 1, then reduce dose to 250 mg twice daily
Gastritis, gastric or duodenal ulcer	≥ Grade 3	
 • Hold (interrupt) dexamethasone until ≤ grade 1 • Reduce dexamethasone by 1 dose level and restart
Edema	≥ Grade 3	
 • Reduce dexamethasone by 1 dose level • Use diuretics as needed
Confusion or mood alternations	≥ Grade 2	
 • Hold (interrupt) dexamethasone until ≤ grade 1 • Reduce dexamethasone by 1 dose level and restart
Muscle weakness	≥ Grade 3	
 • Reduce dexamethasone by 1 dose level • If symptoms persist continue to reduce dexamethasone by 1 dose level as needed.

Toxicity	NCI Toxicity Grade	Action
Hyperglycemia	≥ Grade 3	
 Reduce dexamethasone by 1 dose level Treat with insulin or oral hypoglycemics as needed
Acute pancreatitis	≥ Grade 3	
 Discontinue dexamethasone and patient off study.
Other non-hematologic toxicity assessed as treatment-related	≥ Grade 3	
 Attribute toxicity to one or more drugs. Hold drug(s) attributed to toxicity for remainder of cycle. Reduce drug(s) attributed to toxicity by 1 dose level.*

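### BiRd arm: the diarrhea and appetite loss/nausea rows fix the clarithromycin restart at 250 mg twice daily, so a repeat grade 3 or higher event at that dose brings no reduction

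*Combined protocol and SAP*

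**What the plan says.** Table 1 in Section 9.6 sets out a clarithromycin ladder. The starting dose is 500 mg twice daily. Level -1 is "250 mg BID PO days 1-28 of a 28 day cycle" and Level -2 is "250 mg PO daily on days 1-28 of a 28 day cycle". Level -3 is 250 mg on odd days, and Level -4 is discontinuation.

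Table 2b gives the BiRd actions by toxicity. The diarrhea row and the loss of appetite or nausea row, both at grade 3 or higher, carry the same instruction: "Hold (interrupt) clarithromycin until ≤ grade 1, then reduce dose to 250 mg twice daily".

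The dyspepsia row, also at grade 3 or higher and also involving clarithromycin, uses a relative step: "Reduce dexamethasone OR clarithromycin by 1 dose level based on attribution and restart dexamethasone and clarithromycin". The muscle weakness row provides for persistence: "If symptoms persist continue to reduce dexamethasone by 1 dose level as needed".

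The general text of Section 9.6 says "Doses must be adjusted for adverse events deemed related to study drug by the investigator". It gives the investigator discretion in these terms: "Doses may be adjusted for adverse events related to study medications not listed below at the discretion of the investigator". Under Section 9.5, if a drug was omitted for the rest of a cycle, or the next cycle is delayed by new toxicity, "then the new cycle will be started with dose modifications as described in Section 9.6 and Table 2".

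**The concern.** The two rows name a dose where they should name a step. The named dose is a reduction for a patient on 500 mg twice daily. For a patient already on 250 mg twice daily, the row amounts to a hold followed by re-challenge at the dose on which the event occurred. These rows never lead to Levels -2, -3 or -4.

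A patient can be at Level -1 because of an earlier event under either row, or through the dyspepsia row, the catch-all row for other non-hematologic toxicity, or a discretionary reduction for an unlisted event.

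Section 8.1 lists diarrhea and nausea among the common effects of clarithromycin, so the rows govern expected toxicities of the drug under test. Table 2a has no diarrhea or nausea row. In the Rd arm such events fall under the catch-all row, which takes one level off each time. The rule for a repeat event is therefore complete in the control arm and missing in the arm with the added drug. Sites left to improvise may also differ from one another, and relative dose intensity of each component is a study objective (Section 2.1.6).

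**Working it through.** **Inputs.** The dose levels come from Table 1 and the row actions from Table 2b, both in Section 9.6. The plan states no figure on this point to reproduce.

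**Scheduled clarithromycin per full 28-day cycle** (mg per dose × doses per day × days):

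- Start: 500 × 2 × 28 = 28,000 mg
- Level -1: 250 × 2 × 28 = 14,000 mg
- Level -2: 250 × 1 × 28 = 7,000 mg
- Level -3: 250 × 14 odd days = 3,500 mg
- Level -4: 0 mg

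**One event, by the level at which it occurs:**

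| Level at event | Before (mg) | After, row as written (mg) | After, one-level step (mg) |
|---|---|---|---|
| Start | 28,000 | 14,000 (-50%) | 14,000 (-50%) |
| -1 | 14,000 | 14,000 (0%) | 7,000 (-50%) |
| -2 | 7,000 | 14,000 (+100% if read literally) | 3,500 (-50%) |
| -3 | 3,500 | 14,000 (+300% if read literally) | 0 |

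At Level -1 the difference is 14,000 - 7,000 = 7,000 mg per cycle. At Levels -2 and -3 the named dose exceeds the current one and contradicts the instruction to reduce. Sites would be unlikely to escalate, but the row then gives them nothing usable.

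**Successive events managed through these two rows alone.** After events 1, 2, 3 and 4 the written rule gives 14,000 mg each time. A one-level rule gives 14,000, 7,000, 3,500 and 0 mg.

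**Comparison with the rest of Table 2b.** The table has 23 rows, of which 15 order a dose reduction.

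- Relative step (13 rows): neutropenia with fever, grade 4 neutropenia, thrombocytopenia, non-blistering rash, arrhythmia of grade 2 or higher, allergic reaction of grade 2 or higher, dyspepsia, gastritis or ulcer, edema, confusion or mood, muscle weakness, hyperglycemia, and other non-hematologic toxicity.
- Fixed dose (2 rows): diarrhea, and loss of appetite or nausea.

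**Whether other text supplies the step:**

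- The mandatory-adjustment sentence in Section 9.6 gives no step size. At Level -1 it conflicts with the row.
- The discretion sentence is limited to events outside the tables. These toxicities are listed for BiRd.
- The catch-all row covers toxicities other than those listed.
- Section 9.5 refers back to Section 9.6 and Table 2.

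**The case against.** The best reply is that the plan, read as a whole, points to a further step down. Section 9.6 makes Table 1 operative along with Tables 2a and 2b. Both rows use the verb reduce, and a restart at an unchanged dose is not a reduction. Section 9.5, naming clarithromycin, describes a drug halted and then restarted one level lower, and carries that lower dose into the next cycle. Section 4.1 expects reasonable attempts at dose reduction before removal. An investigator would probably step down. This is a fair account of likely intent and practice, but it does not give the instruction. The Section 9.5 sentence is conditional: it carries forward a one-level reduction already made and does not order one.

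The row count can also be challenged. Eleven of the 13 relative-step rows name only lenalidomide or dexamethasone. Both neutropenia rows also allow growth factor support with the lenalidomide dose kept. The thyroid and venous thrombosis rows deliberately resume at the same dose. All of this is correct, so the count shows inconsistency of style and does not by itself prove an error. But where the table wants the same dose, it says so. The diarrhea and nausea rows order a reduction. The closest comparator, dyspepsia, uses a step for the same drug.

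Finally, the four-event sequence needs repeated severe events, literal compliance each time, and no decision to stop clarithromycin. The hold also lowers the dose actually received. That sequence shows what the rule says and does not forecast what patients would receive.

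**Conclusion.** The concern holds, as a minor one. As written, a grade 3 or higher event under either row in a patient already on 250 mg twice daily leads to a restart at the same dose: 0% reduction instead of 50%, or 7,000 mg more per full cycle than a one-level step. Two of the 15 dose-reducing rows are affected.

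The per-cycle figures are scheduled doses after restart, taken from Table 1, and assume that the row is followed literally. The documents give no event rates, so the number of patients is unknown and could be zero.

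The reach is limited to the BiRd arm before maintenance, because the maintenance regimen in Section 9.1 does not list clarithromycin. Harm is limited because one agent can be stopped while the others continue (Section 4.1) and a patient can be removed (Section 10.11). Sample size, power and error rate are not affected.

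**What to change.** In both rows, replace the fixed dose with an instruction to reduce clarithromycin by one dose level from the current one, citing Table 1. State that an event at Level -3 leads to discontinuation (Level -4). Keep the hold until grade 1 or lower.

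Optionally, add to the BiRd diarrhea row that diarrhea attributed to lenalidomide follows the catch-all row, as the attribution text in Section 9.6 already implies.

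The cost is rewording two table rows, which can go into the next amendment. Sites would have to look up the current dose level instead of reading off one dose. The first-event action stays at 500 to 250 mg twice daily, and no procedures are added.

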10.0 STUDY EVALUATIONS

Patients will be followed in clinic every week for the first cycle and on Day 1 (+/- 7 days) for subsequent cycles. Females of childbearing potential (FCBP) must have a pregnancy test done by the doctor as outlined in Appendix III prior to and during lenalidomide-containing cycles. During scheduled study visits patients will undergo the following evaluations for assessment of response and toxicity (depicted in Table 1, section 1.0):

10.1 Day 1, Cycle 1

- Physical evaluation: A complete medical evaluation including medical history, concomitant medications, physical exam, vital signs, KPS, height and weight.
- Complete Blood Count (CBC) with differential and platelet count
- Complete metabolic profile (including sodium, potassium, chloride, CO₂, calcium, blood urea nitrogen (BUN), creatinine, glucose, albumin, total protein, alkaline phosphatase, total bilirubin, SGOT/AST, and SGPT/ALT)
- Lactate dehydrogenase (LDH)
- Uric Acid
- Magnesium
- Phosphorus
- Drug diary generated and reviewed with patient (See Appendix VIII)
- Serum protein electrophoresis, serum immunofixation, serum quantitative immunoglobulins
- Serum free light chain studies
- 24-hour urine collection for total protein, protein electrophoresis, and immunofixation
- Serum pregnancy test, if applicable
- Quality of Life Assessment (See Appendix IX)

10.2 Days 8, 15, 22 Cycle 1

- Complete Blood Count (CBC) with differential and platelet count
- Complete metabolic profile (including sodium, potassium, chloride, CO₂, calcium, blood urea nitrogen (BUN), creatinine, glucose, albumin, total protein, alkaline phosphatase, total bilirubin, SGOT/AST, and SGPT/ALT, LDH, uric acid)

10.3 Day 1 (starting cycle 2) and End of Study

- Physical evaluation: A complete medical evaluation including medical history, adverse events, concomitant medications, physical exam, vital signs, KPS, height and weight.
- Complete Blood Count (CBC) with differential and platelet count.
- Complete metabolic profile (including sodium, potassium, chloride, CO₂, calcium, blood urea nitrogen (BUN), creatinine, glucose, albumin, total protein, alkaline phosphatase, total bilirubin, SGOT/AST, SGPT/ALT
- LDH
- Uric Acid
- TSH every 3 months beginning with cycle 4 (more often if clinically indicated)
- Serum protein electrophoresis, serum immunofixation, serum quantitative immunoglobulins
- Serum free light chains studies
- 24-hour urine collection for total protein, protein electrophoresis, and immunofixation.
- Prior cycle drug diary will be collected. New drug diary will be generated and reviewed with the patient.
- Serum pregnancy test, if applicable
- Bone marrow aspiration and biopsy to confirm a CR, or when clinically indicated.
- Skeletal survey, MRI, or whole body PET/CT scan when clinically indicated (i.e., to evaluate for disease response in non-secretory myeloma or to investigate for disease progression).
- All subjects will be followed for survival. Cause of death is to be recorded in the subject's medical record.
- Quality of Life assessment (Appendix IX)
- Second primary malignancies will be monitored as events of interest and should be included as part of the assessment of adverse events throughout the course of the study.

10.4 Post Study Follow-up

All attempts will be made to follow patients until progression or death. Subjects who have been discontinued from study will still be followed in a clinic setting to the fullest extent possible on a monthly to bi-monthly basis. Those who choose not to resume regular clinic follow-up will be contacted every 6 months by telephone or electronically

to collect post study information. The post-study collection information will consist of a telephone interview between the clinical investigator and the discontinued patient. The information requested will be current disease status including information about the development of secondary primary malignancies, current treatment use, and physical status of the patient.

10.5 Treatment Compliance

At all times research center personnel will review the dosing instructions with subjects. Subjects will be asked to maintain a drug diary to record the drug administration. If doses of clarithromycin or lenalidomide are missed, the dose should be taken as soon as possible on the same day. If the dose is missed for the entire day, it should not be made up. Missed doses of dexamethasone will not be made up. Vomited doses of clarithromycin, lenalidomide and dexamethasone will not be made up. Patients who take more than the prescribed dose of clarithromycin, lenalidomide or dexamethasone should be instructed to seek emergency medical care if needed and contact study staff immediately. Subjects will be asked to bring any unused study drug to the research center at their next visit. Research personnel will count and record the number of used and unused study drug capsules at each visit.

10.11 Criteria for removal from study

Rules for termination of the study for the individual subject are listed below:

- Subjects may withdraw consent and stop participation at any time.
- Any Grade 4 skin toxicity (i.e. Stevens Johnson syndrome) or Grade 4 hypersensitivity (i.e. anaphylaxis).
- Progression of multiple myeloma, as defined by the International Myeloma Working Group Criteria (Appendix 1 of the protocol).
- Development of any co-morbid condition or excessive toxicity that would make further participation in the protocol unsafe.
- The development of any comorbid condition of excessive toxicity that would make further participation in the protocol unsafe.
- Non-compliance or refusal of the patient to continue treatment and/or evaluation.
- Major violation of the study protocol.
- Any adverse event(s) that, in the judgment of an Investigator, may cause severe or permanent harm if the study medications are continued.
- At the discretion of the principal investigator and/or Celgene Pharmaceuticals, Inc. for any reason.
- Loss to follow up.
- Death of patient

Any possible premature discontinuation would be documented adequately with reasons being stated, and information would have to be issued according to local requirements (e.g., IRB/EC, regulatory authorities, etc.).

10.11.2 The responsible Clinical Investigator as well as Celgene Pharmaceuticals, Inc. have the right to discontinue this study at any time for reasonable medical or administrative reasons in any single center. Possible reasons for termination of the study could be but are not limited to:

- Unsatisfactory enrollment with respect to quantity or quality.
- Inaccurate or incomplete data collection.
- Falsification of records.
- Failure to adhere to the study protocol.

11.0 ADVERSE EVENTS GRADING AND REPORTING

11.1 Adverse Events

An adverse event is any sign, symptoms, illness, or diagnosis (either observed or volunteered) that appears or worsens during the course of the study. Toxicity will be scored using CTCAE version 4.0 for toxicity and adverse event reporting. A copy of the CTCAE version 4.0 can be downloaded from the CTEP homepage

<http://ctep.info.nih.gov>. All appropriate treatment areas must have access to a copy of the CTCAE version 4.0. All adverse clinical experiences, whether observed by the investigator or reported by the patients, must be recorded with details about the duration and intensity of each episode, the action taken with respect to the test drug, and the patient's outcome. The investigator must evaluate each adverse experience for its relationship to the test drug and for its seriousness.

The investigator must appraise all abnormal laboratory results for their clinical significance. If any abnormal laboratory result is considered clinically significant, the investigator must provide details about the action taken with respect to the test drug and about the patient's outcome.

11.2 Serious Adverse Events (SAE)

A serious adverse event is one that at any dose (including overdose):

- Results in death
- Is life-threatening¹
- Requires inpatient hospitalization or prolongation of existing hospitalization
- Results in persistent or significant disability or incapacity²
- Is a congenital anomaly or birth defect
- Is an important medical event³
- Suspected or positive pregnancy

¹“Life-threatening” means that the subject was at immediate risk of death at the time of the serious adverse event; it does not refer to a serious adverse event that hypothetically might have caused death if it were more severe.

²“Persistent or significant disability or incapacity” means that there is a substantial disruption of a person’s ability to carry out normal life functions.

³Medical and scientific judgment should be exercised in deciding whether expedited reporting is appropriate in situations where none of the outcomes listed above occurred. Important medical events that may not be immediately life-threatening or result in death or hospitalization but may jeopardize the patient or may require intervention to prevent one of the other outcomes listed in the definition above should also usually be considered serious. Examples of such events include allergic bronchospasm requiring intensive treatment in an emergency room or at home, blood dyscrasias or convulsions that do not result in inpatient hospitalization, or the development of drug dependency or drug abuse. A new diagnosis of cancer during the course of a treatment should be considered as medically important.

Second primary malignancies will be monitored as events of interest and must be reported as serious adverse events regardless of the treatment arm the subject is in. This includes any second primary malignancy, regardless of causal relationship to any of the study drugs, occurring at any time for the duration of the study, from the time of signing the informed consent up to the time all patients have been followed for at least 5 years from randomization or have died. Events of second primary malignancy are to be reported using the SAE report form and must be considered an “Important Medical Event” even if no other serious criteria apply; these events must also be documented in the appropriate page(s) of the CRF and subject’s source documents.

Documentation on the diagnosis of the second primary malignancy must be provided at the time of reporting as a serious adverse event (eg., any confirmatory histology or cytology results, X-rays, CT scans, etc.).

11.2.1 Pregnancies:

Pregnancies and suspected pregnancies (including a positive pregnancy test regardless of age or disease state) of a female subject occurring while the subject is on lenalidomide, or within at least 28 days of the subject’s last dose of lenalidomide, are considered immediately reportable events. Lenalidomide is to be discontinued immediately. The pregnancy, suspected pregnancy, or positive pregnancy test must be reported to Celgene Drug Safety immediately by facsimile, or other appropriate method, using the Pregnancy Initial Report Form, or approved equivalent form. The female subject should be referred to an obstetrician-gynecologist, preferably one experienced in reproductive toxicity for further evaluation and counseling.

The Investigator will follow the female subject until completion of the pregnancy, and must notify Celgene Drug Safety immediately about the outcome of the

pregnancy (either normal or abnormal outcome) using the Pregnancy Follow-up Report Form, or approved equivalent form. If the outcome of the pregnancy was abnormal (e.g., spontaneous or therapeutic abortion), the Investigator should report the abnormal outcome as an AE. If the abnormal outcome meets any of the serious criteria, it must be reported as an SAE to Celgene Drug Safety immediately by facsimile, or other appropriate method, within 1 business day of the Investigator's knowledge of the event using the SAE Report Form, or approved equivalent form.

All neonatal deaths that occur within 28 days of birth should be reported, without regard to causality, as SAEs. In addition, any infant death after 28 days that the Investigator suspects is related to the in utero exposure to lenalidomide should also be reported to Celgene Drug Safety immediately by facsimile, or other appropriate method, within 1 business day of the Investigator's knowledge of the event using the SAE Report Form, or approved equivalent form.

Male Subjects

If a female partner of a male subject taking lenalidomide becomes pregnant, the male subject taking lenalidomide should notify the Investigator, and the pregnant female partner should be advised to call their healthcare provider immediately.

11.2.2 Celgene Drug Safety Contact Information for Pregnancy Reporting:

Celgene Corporation
Drug Safety
[name]
[name]

Toll Free: [contact]
[contact]
[contact]
Email: [contact]

11.3 Investigator Reporting Responsibilities:

The conduct of the study will comply with all FDA safety reporting requirements.

All adverse experience reports must include the patient number, age, sex, weight, severity of reaction (mild, moderate, severe), relationship to study drug (probably related, unknown relationship, definitely not related), date and time of administration of test medications and all concomitant medications, and medical treatment provided. The investigator is responsible for evaluating all adverse events to determine whether criteria for "serious" and "unexpected" as defined above are present. The investigator is responsible for reporting adverse events to Celgene as described below.

